11.2 Radiographic Tumor Response Criteria

11.2.1 Stratum 1

Stratum 1: Response and progression for vestibular schwannomas will be evaluated in this study using the Response Evaluation in Neurofibromatosis and Schwannomatosis (REiNS) criteria proposed by Widemann and colleagues for neurofibromatosis-associated lesions..⁴⁶ Response and progression for stratum 1 will not be evaluated using the Response Evaluation Criteria in Solid Tumors (RECIST) or by MacDonald Criteria, since they may underestimate progression in these irregularly shaped tumors. However, linear measurements utilizing RECIST will be collected as part of the trial for comparison with volumetric measurements. Linear measurements utilizing RECIST will be used for non-target lesions on stratum 1.

Target lesions. Investigators should identify a single target lesion in all subjects. The target lesion in this study is the progressive VS (i.e. the lesion that is enlarging or is associated with hearing loss) that led to registration in the protocol. In cases where subjects have a single ear with hearing, the target lesion should be the enlarging VS ipsilateral to the hearing ear. In cases where subjects have hearing in both ears, the target lesion should be the tumor associated with word recognition score < 85% and is growing the fastest or is causing the most rapid hearing loss. In cases where both VSs are associated with word recognition < 85% and progressing equally rapidly, the target lesion should be the larger of the two tumors on imaging. Target lesions should be identified at baseline and measured using volumetric analysis of the baseline MRI scan. The baseline volumetric MRI scan will be used as reference for comparison of all

future MRI scans to characterize the objective tumor response.

Non-target lesions. Non-target lesions in this study include VSs contralateral to the target lesion (if present).

Volumetric analysis of MRI scans should be performed on sequences with fine cuts through the internal auditory canal

NOTE: Histologic confirmation of tumor type is not required.

11.2.1.1 Evaluation of Target Lesion

Target lesions defined in section 11.2.1 (REiNS criteria)

Radiographic Response (RR)

At least a 20% decrease in the volume of the target lesions, taking as reference the baseline volume.

Progressive Disease (PD)

At least a 20% increase in the volume of the target lesion, taking as reference the lower volume during treatment

Stable Disease (SD)

Does not meet criteria for radiographic response or for progressive disease.

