11.2.1.2 Evaluation of Non Target Lesions

Non-Target lesions defined in section 11.2.1 (RECIST criteria)

Complete Response (CR): Disappearance of all non-target lesions and normalization of tumor marker level

Incomplete Response/ Stable Disease (SD): Persistence of one or more non-target lesion(s) or/and maintenance of tumor marker level above the normal limits

Progressive Disease (PD): Appearance of one or more new lesions and/or unequivocal progression of existing non-target lesions

Duration of radiographic response: The duration of radiographic response is measured from the time measurement criteria are met for RR until the first date that progressive disease is objectively documented (taking as reference for progressive disease the lowest tumor volume during treatment).

Duration of stable disease: Stable disease is measured from the start of the treatment until the criteria for progression are met, taking as reference the measurements recorded at baseline.

11.2.2 Stratum 2 Tumor Response Criteria:

Stratum 2 Response and progression for non-VS tumor by MacDonald Criteria.

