11.2.2.2 Partial Response

Partial Response (PR): Greater than or equal to 50% reduction in tumor size by bidimensional measurement, as compared with the baseline measurements, on a stable or decreasing dose of corticosteroids, accompanied by a stable or improving neurologic examination, and maintained for at least 8 weeks.

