11.2.2.3 Stable Disease

Stable Disease (SD): Neurologic exam is at least stable and maintenance corticosteroid dose not increased, and MR/CT imaging meets neither the criteria for PR nor the criteria for Progressive Disease. If this category is to be reported as of possible clinical benefit, Stable Disease status must be maintained for 6 courses.

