11.2.2.4 Progressive Disease

Progressive Disease (PD): Progressive neurologic abnormalities or worsening neurologic status not explained by causes unrelated to tumor progression (e.g., anticonvulsant or corticosteroid toxicity, electrolyte disturbances, sepsis, hyperglycemia, etc.), OR a greater than 25% increase in the bi-dimensional measurement, taking as a reference the smallest disease measurement recorded since the start of protocol therapy, OR the appearance of a new lesion, OR increasing doses of corticosteroids required to maintain stable neurological status or imaging AND/OR unequivocal radiological progression of existing non-target lesions.

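### The reference for progression by size differs within Stratum 1 and, read literally, leaves out the pre-therapy scan in Stratum 2 (minor)

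*Combined protocol and SAP*

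**What the plan says.** **Stratum 1.** Section 11.2.1.1 measures radiographic response of the target vestibular schwannoma against baseline volume. It defines progressive disease (PD) as "At least a 20% increase in the volume of the target lesion, taking as reference the lower volume during treatment". In section 11.2.1.2, the line on duration of radiographic response uses the same reference, "taking as reference for progressive disease the lowest tumor volume during treatment". The next line, on duration of stable disease (SD), counts time "until the criteria for progression are met, taking as reference the measurements recorded at baseline".

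**Stratum 2.** Section 11.2.2 states "Stratum 2 Response and progression for non-VS tumor by MacDonald Criteria" and then writes out its own definitions. Partial response (11.2.2.2) is judged "as compared with the baseline measurements". PD by size (11.2.2.4) needs growth of more than 25% in the bidimensional measurement, "taking as a reference the smallest disease measurement recorded since the start of protocol therapy". No Stratum 2 progression text names baseline.

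**Scan timing.** Under section 9.1.3 the first MRI is done before therapy and the next ones after courses 3, 6, 9, 12, 16, 20 and 26. Section 3.4 allows eligibility imaging up to four weeks before registration and a start of therapy up to 14 days after it.

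**Use of the definitions.** Section 5.3 requires at least stable disease and no progression before each course. Section 5.6.3 takes patients off treatment for progression as defined in 11.1 and 11.2.

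**The concern.** A progression rule needs one stated reference measurement. In Stratum 1 the same criteria are given two: the lowest on-treatment volume and the baseline volume. Two readers can therefore classify the same series of scans differently and both be following the protocol.

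In Stratum 2 the written reference begins with the start of therapy, and the baseline MRI is taken before that. Taken at its word, the rule has nothing earlier to compare with at the first on-treatment scan. A tumour that never shrinks is later compared with its own enlarged size.

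At stake are:
- whether a patient continues selumetinib (5.3, 5.6.3);
- the response category (13.1.2) and the recorded progression date (5.6);
- the length of stable disease in Stratum 1;
- in Stratum 2, the conditional benefit statement in 11.2.2.3: "If this category is to be reported as of possible clinical benefit, Stable Disease status must be maintained for 6 courses".

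**Working it through.** The plan states no figure on this point, so there is nothing to reproduce. The check applies each written rule to the same measurements. All tumour sizes below are illustrations; the protocol gives no on-study growth rates.

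**Inputs from the protocol**
- Stratum 1 size PD: ratio to reference of at least 1.20 (11.2.1.1).
- Stratum 1 radiographic response: ratio to baseline of 0.80 or less (11.2.1.1).
- Stratum 2 size PD: ratio to reference above 1.25 (11.2.2.4).
- First two on-treatment scans: after course 3 (3 × 4 = week 12) and course 6 (6 × 4 = week 24).
- Baseline scan: up to 4 + 2 = 6 weeks before the first dose (3.4).

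**Stratum 1: shrinkage of less than 20%, then regrowth.** Volumes 2.0 cc (baseline), 1.7 cc (week 12), 2.1 cc (week 24).
- Week 12: 1.7/2.0 = 0.85, a 15% decrease. This is not a radiographic response, so the patient is stable.
- Week 24 by 11.2.1.1 (lowest on-treatment volume): 2.1/1.7 = 1.24, at least 1.20, so PD.
- Week 24 by the stable-disease line of 11.2.1.2 (baseline): 2.1/2.0 = 1.05, below 1.20, so still stable.

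In general, after shrinkage by a fraction s, the on-treatment reference calls PD at (1 − s) × 1.20 of baseline, while the baseline reference calls it at 1.20:

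| Shrinkage s | PD level, on-treatment reference | PD level, baseline reference |
|---|---|---|
| 5% | 0.95 × 1.20 = 1.14 | 1.20 |
| 10% | 0.90 × 1.20 = 1.08 | 1.20 |
| 15% | 0.85 × 1.20 = 1.02 | 1.20 |

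Between the two levels the texts disagree. For s = 15% and a 2.0 cc baseline, that is from 2.04 cc up to 2.40 cc.

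For a responder the lowest volume is at most 0.80 of baseline, so it is always an on-treatment value. Adding baseline to the reference set leaves duration of radiographic response unchanged.

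**Stratum 2: growth only.** Area 1.00 (baseline), 1.30 (week 12), 1.60 (week 24).
- Literal text, week 12: the only measurement since therapy began is this one, so no ratio can be formed.
- Literal text, week 24: 1.60/1.30 = 1.23, not above 1.25, so no PD by size. Week 24 also completes six courses, so the patient could be counted as stable for that long if no other progression route applies.
- Baseline included, week 12: 1.30/1.00 = 1.30, above 1.25, so PD.

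**Primary endpoints.** The Stratum 1 endpoint uses the baseline word recognition score. The Stratum 2 endpoint is complete plus partial response, judged by disappearance of tumour or against baseline. Neither definition uses the progression reference, and nor do the two-stage rules in 13.2 (9 + 8 patients).

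**The case against.** The strongest reply is that no experienced reader would leave baseline out. Section 5.3 demands a progression decision before every course, baseline is the only scheduled scan before week 12, and the protocol names published criteria (REiNS, MacDonald) that may settle the matter. In Stratum 1 the texts can also be read together as lowest volume after shrinkage and baseline otherwise, which deals with a tumour that only grows. Stable-disease duration serves no listed objective. Other progression routes remain: hearing loss, new lesions and non-target progression in Stratum 1; neurologic worsening, new lesions, steroid need and non-target progression in Stratum 2.

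Much of this stands, and it keeps the point small. It does not remove it. The protocol writes out its own definitions and names baseline where it wants baseline. The cited criteria cannot be checked from the documents. The combined reading still leaves the 2.0, 1.7, 2.1 cc patient with two answers.

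A reader might infer more than the documents support:
- *That section 11.2.1 is a further conflict.* Its sentence beginning "The baseline volumetric MRI scan will be used as reference for comparison of all" goes on to limit itself to objective tumour response. That agrees with measuring response from baseline and does not define progression.
- *That an investigator might use baseline at week 12 and then drop it, letting still larger growth pass at week 24.* Someone who counts baseline as the smallest value at week 12 has no reason to discard it while it is still the smallest.
- *That progression would be delayed by a stated number of weeks.* Any such figure needs an assumed growth rate on drug. In addition, growth slow enough to reach size PD only at week 104 (26 × 4) has no stopping consequence, because treatment ends then anyway.

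**Conclusion.** The concern holds as a minor wording defect. In Stratum 1 the two references give opposite calls for a tumour that shrinks by less than 20% and regrows (1.24 against 1.05 in the example). In Stratum 2 the literal text allows growth from the pre-therapy scan to go uncalled by size (1.23 in the example, against 1.30 from baseline at week 12). The Stratum 2 part assumes a literal reading. Many investigators would include baseline, and for them nothing is missed.

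The effect is confined to the PD or SD category, the progression date, stable-disease duration and treatment stopping. A reader might infer that the main efficacy conclusions are at risk. They are not on this account: both primary endpoint definitions, the sample size, alpha and power do not depend on the reference, and section 1.2 lists no progression-free survival or disease-control objective. Frequency is unknown, since the documents give no on-study growth rates and entry does not require growth in size.

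**What to change.** In 11.2.1.1 and 11.2.2.4, define the reference for progression as *the smallest measurement recorded at baseline or at any later scan*. Use the same reference in the duration-of-stable-disease line of 11.2.1.2. In the examples above, this rule calls PD in both strata.

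The cost is a few words in two definitions and one aligned line, with no new data and no change to sample size, alpha or power.

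There is a small downside. Some patients may meet progression by size and stop earlier than under the literal text. In Stratum 1 this could happen before the week-24 hearing test, because hearing evaluations run only until progression or end of therapy (section 10, note C). The clinical team should confirm that consequence in the same amendment.

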11.2.1.2 Evaluation of Non Target Lesions

Non-Target lesions defined in section 11.2.1 (RECIST criteria)

Complete Response (CR): Disappearance of all non-target lesions and normalization of tumor marker level

Incomplete Response/ Stable Disease (SD): Persistence of one or more non-target lesion(s) or/and maintenance of tumor marker level above the normal limits

Progressive Disease (PD): Appearance of one or more new lesions and/or unequivocal progression of existing non-target lesions

Duration of radiographic response: The duration of radiographic response is measured from the time measurement criteria are met for RR until the first date that progressive disease is objectively documented (taking as reference for progressive disease the lowest tumor volume during treatment).

Duration of stable disease: Stable disease is measured from the start of the treatment until the criteria for progression are met, taking as reference the measurements recorded at baseline.

11.2.2 Stratum 2 Tumor Response Criteria:

Stratum 2 Response and progression for non-VS tumor by MacDonald Criteria.

11.2.2.1 Complete Response

Complete disappearance on MR of all enhancing tumor and mass effect, on a stable or decreasing dose of corticosteroids (or receiving only adrenal replacement doses), accompanied by a stable or improving neurologic examination, and maintained for at least 8 weeks.

11.2.2.2 Partial Response

Partial Response (PR): Greater than or equal to 50% reduction in tumor size by bidimensional measurement, as compared with the baseline measurements, on a stable or decreasing dose of corticosteroids, accompanied by a stable or improving neurologic examination, and maintained for at least 8 weeks.

11.2.2.3 Stable Disease

Stable Disease (SD): Neurologic exam is at least stable and maintenance corticosteroid dose not increased, and MR/CT imaging meets neither the criteria for PR nor the criteria for Progressive Disease. If this category is to be reported as of possible clinical benefit, Stable Disease status must be maintained for 6 courses.

11.2.2.4 Progressive Disease

Progressive Disease (PD): Progressive neurologic abnormalities or worsening neurologic status not explained by causes unrelated to tumor progression (e.g., anticonvulsant or corticosteroid toxicity, electrolyte disturbances, sepsis, hyperglycemia, etc.), OR a greater than 25% increase in the bi-dimensional measurement, taking as a reference the smallest disease measurement recorded since the start of protocol therapy, OR the appearance of a new lesion, OR increasing doses of corticosteroids required to maintain stable neurological status or imaging AND/OR unequivocal radiological progression of existing non-target lesions.

12 RECORDS, REPORTING, AND DATA AND SAFETY MONITORING

This trial will be conducted in compliance with the protocol, Good Clinical Practice (GCP) and the applicable regulatory requirements.

12.1 Regulatory and Compliance Monitoring

Monitoring of clinical studies is a continuous, ongoing review of the conduct of the trial to ensure that it is conducted, documented, and reported in accordance with the IRB-approved protocol, Title 21 CFR, the International Conference on Harmonisation (ICH) Good Clinical Practice (GCP) Guidelines, and applicable regulatory requirements of the sponsor, CCHMC.

Monitoring will include review of central elements defined as:

- Data related to primary study endpoints;
- Appropriateness of consent documentation;
- Protocol eligibility;
- Protocol compliance;
- Timeliness of data entry, including the reporting of adverse events (AE/SAR) and serious

advent events (SAESSAR) as events are reported;

- Appropriateness of treatment delivery;
- Modifications in dose or timing;
- Investigational Drug Service (IDS) compliance (drug accountability);
- Documentation of response assessment measures;
- Essential regulatory documentation; and
- Site Investigator supervision of overall conduct of the study.

Specifically, source document verification of eligibility for all enrolled study participants including verification of appropriate documentation of consent will be performed. 100% Source Document Verification (SDV) of case records will be conducted for the first 2 participants enrolled on the study, as well as, 4 - 5 randomly selected participants thereafter, by comparing data in the source documents to data entered in the Case Report Forms (CRF). In addition, 100% SDV may be performed for pivotal clinical parameters related to primary study endpoints.

Regulatory and compliance monitoring will be a combination of on-site visits (scheduled to occur at least annually or more frequently based on registration, the degree of risk or severity of monitoring findings, and other study management issues) along with off-site continuous (remote) efforts.

12.2 Responsibility for Data Submission

All participant data will be recorded on case report forms by CCHMC study personnel.

12.3 Data and Safety Monitoring Plan

This study will be reviewed in accordance with the CCHMC Cancer Center Data and Safety Monitoring Plan for Phase 1, Pilot, and Phase 2 Studies. In brief, the role of the CCHMC Cancer Center Data and Safety Monitoring Board (DSMB) is to protect the interests of participants and the scientific integrity of clinical trials. The DSMB consists of individuals with recognized expertise in oncology, radiation therapy, conduct of clinical trials, and biostatistics. The DSMB meets a minimum of twice per year. Approximately 4 weeks before each meeting of the DSMB, the study chair and/or designee will be responsible for preparing study reports for review by the DSMB. The DSMB will provide recommendations to change the study or to continue the study unchanged.

12.4 Oversight by the Sponsor Investigator/Study Chair

The Sponsor Investigator/Study Chair along with the CCHMC coordinating center will review trial progress regularly.

This ongoing review by the Sponsor Investigator/Study Chair or designee will include verification of trial eligibility and the appropriateness of documentation of the informed consent process for all patients to confirm registration into the study prior to the first dose of investigational agent. In the event that the study chair is not available, an appointed designee will review eligibility to confirm registration.

In addition, the Sponsor Investigator/Study Chair and/or designee will review participant trial progress in real-time including participant evaluability, dose modifying toxicities, and serious adverse events.

12.5 Privacy and Confidentiality

No information provided from individual patient records may be discussed with anyone other than those individuals involved in the research study or clinical care. Data may not be released in any form except as stated in the agreement or regulations. Each participant enrolled will, from that point forward, be identified by a unique identifier (study number). This study number will also be used for any research specimens collected and shipped to analysts outside CCHMC (if applicable).

All research records generated will be stored in a locked office area, only accessible to study personnel, and/or on a secure CCHMC network drive and/or the coordinating centers clinical trial management system (OnCore). Clinical information will be accessed, according to HIPAA requirements, by study personnel to complete study documents, as needed.

12.6 Record Retention

Study records will be maintained per applicable regulatory requirements and institutional policies and procedures.

13 STATISTICAL CONSIDERATIONS

13.1 Evaluability

13.1.1 Evaluability for toxicity

All patients will be evaluable for toxicity from the time of their first treatment with selumetinib.

13.1.2 Evaluability for Response

All patients who receive study drug will be considered evaluable for response.

Each participant should be assigned one of the following categories: 1) hearing response, 2) stable hearing, 3) progressive hearing loss, 4) progressive disease 5) tumor response 6) early death from NF2-related condition, 7) early death from toxicity, 8) early death because of other cause.

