11 MEASUREMENT OF EFFECT

11.1 Hearing Response Criteria (Stratum 1 only)

Hearing is monitored in clinical practice by measuring pure tone thresholds, word recognition scores, brainstem auditory evoked responses (BAERs), and otoacoustic emissions (OAEs).

Pure tone thresholds measure the minimum sound level that an ear can perceive. Thresholds are typically measured at octaves and half-octaves from 250 Hz to 8000 Hz. An average of thresholds at 500, 1000, 2000 and 4000 Hz (PTA) is recommended as a standard outcome measure by the American Academy of Otolaryngology, Head and Neck Surgery (AAO-HNS) for reporting in cases of VS.

Word recognition scores measure the ability to recognize (as opposed to detect) auditory information. Patients are presented a list of 50 words at a fully audible level and the percentage identified correctly is the score. This study will use full 50-item monosyllable lists and standardized recordings.

Because tumors associated with NF2 have benign histology, overall survival is not an appropriate endpoint for clinical trials in this condition. Instead, the goal of treatment is to minimize neurologic morbidity (including hearing loss) and to defer surgical treatments that may cause iatrogenic dysfunction. For this reason, hearing function is the most important way to monitor the activity of new agents designed to treat VSs.

Word recognition is the measure most closely associated with daily hearing function since it measures the ability to comprehend speech. If word recognition quality improves, the patient can converse successfully, even if a hearing aid is needed to make sounds sufficiently loud. Statistical methods have been developed to determine significant changes in this measure. Word recognition scores represent summary scores from a collection of binary endpoints (correct/incorrect responses) and thus follow a binomial distribution (e.g., non-Gaussian

^{**} Please note that Grade 3 asymptomatic elevations of CPK do not require a dose reduction

distribution). Although it is tempting to use a set change in word recognition score (e.g., fifteen percentage points) as a clinical response, this approach is inappropriate given the binomial model of variance. A more rigorous approach involves the use of the 95% (p=0.05) critical difference table⁴⁴. The 95% critical differences for 50-word lists as proposed here have been used in previous studies⁴⁵ and in clinical trials evaluating the effect of drug treatment on hearing.

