- 11.1.1 Hearing Response (HR): Improvement in word recognition score above the 95% critical difference, taking as reference the baseline word recognition score (APPENDIX E)
- 11.1.2 Stable Hearing (SH): Persistence of word recognition score within the 95% critical difference, taking as reference the baseline word recognition score (APPENDIX E)
- 11.1.3 Progressive Hearing Loss (PHL): Decline in word recognition score below the 95% critical difference, taking as reference the baseline word recognition score (APPENDIX E)

Duration of hearing response: The duration of hearing response (HR) is measured from the time that measurement criteria are met for HR until the first date that the word recognition score decreases beneath the upper limit of the 95% critical difference of the baseline word recognition score.

Duration of stable hearing: Stable disease is measured from the start of the treatment until the criteria for progression are met, taking as reference the word recognition score recorded at baseline

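### Does the single-category response list in Section 13.1.2, which overlaps in Stratum 1 and omits stable disease in Stratum 2, put the trial's response results at risk?

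*Combined protocol and SAP*

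**What the plan says.** Section 13.1.2 first sets the denominator: "All patients who receive study drug will be considered evaluable for response". It then requires one code per participant: "Each participant should be assigned one of the following categories: 1) hearing response, 2) stable hearing, 3) progressive hearing loss, 4) progressive disease". The list continues with "5) tumor response 6) early death from NF2-related condition" and two further early-death codes, for toxicity and for other causes. It is not split by stratum and gives neither a ranking of codes nor a time point.

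The outcomes behind the codes are defined in Section 11:

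- **Hearing (11.1).** The section heading limits these criteria to Stratum 1. Response is "Improvement in word recognition score above the 95% critical difference", with baseline as reference. Tumour size plays no part.
- **Stratum 1 imaging (11.2.1).** Target response is "At least a 20% decrease in the volume of the target lesions, taking as reference the baseline volume". Progression is a rise of at least 20% from the lowest volume on treatment. For non-target lesions, progression is "Appearance of one or more new lesions and/or unequivocal progression of existing non-target lesions". Hearing plays no part.
- **Stratum 2 imaging (11.2.2).** There are four outcomes: CR, PR, stable disease and progressive disease. Stable disease requires, among other things, that "MR/CT imaging meets neither the criteria for PR nor the criteria for Progressive Disease".

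Section 13.2 states the primary endpoints and the two-stage decision rules. It does not refer to the list in 13.1.2.

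**The concern.** A rule that allows one code per patient works only if the codes exclude each other and cover every case. These do neither. Hearing and tumour volume are judged independently in Stratum 1, so one patient may have a hearing response and a growing tumour. Two analysts applying 13.1.2 literally could file that patient differently. In Stratum 2 the hearing codes do not apply, and stable disease, an outcome that Section 11.2.2.3 defines, has nowhere to go. Some patients who leave early have no code either, although everyone treated is evaluable.

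The stakes would be real if the primary count were read off this code. With at most 17 patients per stratum and success at 3 responders, moving one responder to another code could reverse a decision. A single code also cannot carry both the hearing outcome and the vestibular schwannoma response of objective 1.2.1.

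**Working it through.** **Step 1: the plan's own figures.** Inputs from Section 13.2: n1 = 9, n2 = 8, stop if 0 of 9 respond, success if 3 or more of 17 respond, null rate 0.05, alternative rate 0.25. Let X1 and X2 be the responders in each stage.

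- Early stopping: P(X1 = 0) = (1 − p)^9. At 0.05 this is 0.95^9 = 0.630 (stated 0.63). At 0.25 it is 0.75^9 = 0.075 (stated 0.075).
- Success: P(X1 + X2 ≥ 3) − P(X1 = 0) × P(X2 ≥ 3).
  - At 0.05: 0.0503 − 0.6302 × 0.0058 = 0.0466 (stated 0.05).
  - At 0.25: 0.8363 − 0.0751 × 0.3215 = 0.8122 (stated 0.81).
- Expected size at 0.05: 9 + (1 − 0.630) × 8 = 11.96 (stated 12).

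All the stated figures reproduce. They depend on the responder counts alone.

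**Step 2: where the list fails as a partition.**

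| Stratum | Outcome of a living patient | Codes met |
|---|---|---|
| 1 | Any hearing result, tumour stable | one of 1–3 |
| 1 | Any hearing result, tumour response | one of 1–3, and 5 |
| 1 | Any hearing result, tumour progression | one of 1–3, and 4 |
| 2 | CR or PR | 5 |
| 2 | Progressive disease | 4 |
| 2 | Stable disease | none |

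This cannot be turned into a share of patients. The documents give no frequencies, and the table is not a full grid of outcomes. Volume response is measured from baseline and progression from the lowest volume, so one patient can have both in turn. A target response can coexist with a new lesion. At baseline word scores of 2% or 4%, which Section 3.1.2.1 admits, Appendix E makes progressive hearing loss impossible.

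**Step 3: patients who stop early.** Note C of the Study Calendar puts the first on-treatment hearing test and MRI after course 3 (3 × 28 days = 12 weeks). The calendar also schedules a brain MRI at completion or discontinuation of treatment, with a spine MRI if clinically indicated; only the hearing evaluation is blank there. An early leaver can therefore be coded for tumour response or progression. Those left without a code are a Stratum 1 patient with a stable discontinuation MRI and no on-treatment hearing test, a Stratum 2 patient with a stable MRI (the gap in Step 2), and any patient with no post-baseline assessment.

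**Step 4: which results use the code.**

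| Result | Defined in | Uses the 13.1.2 code? |
|---|---|---|
| Stratum 1 primary: hearing response at 24 weeks | 13.2, 11.1.1, Appendix E | No |
| Stratum 2 primary: sustained CR + PR | 13.2, 11.2.2.1–11.2.2.2 | No |
| Vestibular schwannoma response | 1.2.1, 11.2.1.1 | No |

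The Stratum 1 endpoint has a matching scheduled test, since course 6 ends at 6 × 28 days = 24 weeks.

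**Step 5: what misuse would cost.** Suppose, against the text, that the single code supplied the Stratum 1 count, and that a share q of hearing responders were filed under a tumour code. The effective rate is then 0.25 × (1 − q). The documents give no value of q, so these are assumed: q = 10%, 20%, 30% and 50% give power of 0.75, 0.66, 0.57 and 0.34. This shows why the question deserved a check. It does not describe what the plan does.

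**The case for a change.** The best case for a change is that the text says one category, not two. If separate hearing and imaging variables are meant, the plan should say so, and the repair costs only some rewording because the assessments are already scheduled. With at most 17 patients per stratum, one doubtful classification is about 6% of a response table (1/17). The overlap also arises over time: hearing is judged at 24 weeks while MRI continues to course 26, so a hearing responder may progress later, and nothing says which code holds. Section 5.6.3 cites both 11.1 and 11.2 for progressive disease, which might blur codes 3 and 4 as well.

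The textual part of this stands: the list is neither exclusive nor exhaustive. The inference to harm does not. The response rates have their own definitions, so a doubtful code alters a descriptive listing and not a rate. The point about 5.6.3 is weak, because that section is an off-treatment rule, while 13.1.2 lists progressive hearing loss and progressive disease as separate codes and only 11.2 defines the latter term.

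**Conclusion.** The mismatch in Section 13.1.2 is genuine but editorial. An analyst following the plan counts Stratum 1 responders from the 24-week word recognition score, Stratum 2 responders from sustained CR plus PR, and vestibular schwannoma responders from the 20% volume criterion. None of these steps passes through the eight-code list, so the decision rules, the error rates of 0.047 and 0.812, and the secondary response rate are the same whether or not the list is tidied.

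This rests on two assumptions. The first is that the counts come from the endpoint definitions; no section directs otherwise. The second is that a treated patient with no usable assessment stays in the denominator and is not a responder. The plan does not spell this out, but it is the natural reading of making all treated patients evaluable while requiring a demonstrated improvement or reduction for response.

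For the descriptive summary, recording hearing and imaging results as separate variables, with stable disease and not assessed as possible values, is ordinary practice and needs no data beyond those scheduled. This is a gap that analysts fill sensibly, and no change to the plan follows.
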